6.8. Study Drug Exposure and Compliance

Exposure to study drug will be summarized by cohort and overall for all patients in the SAF Analysis Set.

Patients will be randomized to receive for a total of 4 weeks BOS-589 at 1 of 2 dose levels or Placebo bid, as described in the following cohorts:

- Cohort 1 (High Dose): 2 x 100 mg tablets for the 200 mg BOS-589 bid orally
- Cohort 2 (Low Dose): 2 x 25 mg tablets for the 50 mg BOS-589 bid orally
- Cohort 3 (Placebo): 2 x visually matched Placebo tablets bid orally

The duration of exposure to study drug is calculated as date of last dose of study drug taken – date of first dose of study drug taken +1.

The planned total number of tablets during exposure is defined as duration of exposure x 4.

Sponsor: Boston Pharmaceuticals, Inc.
Protocol Number: BOS-589-201
Version and Date: Version 1.2 12NOV2020

The actual total number of tablets taken during exposure is calculated as the total number of tablets given – the total number of tablets returned, both collected in the eCRF.

The average actual daily number of tablets taken is calculated as the actual total number of tablets taken during exposure / duration of exposure to study drug.

The drug compliance is calculated as the actual total number of tablets taken during exposure / planned total number of tablets taken during exposure x 100%.

The duration of exposure to study drug, planned and actual total number of tablets during exposure, average actual daily number of tablets taken, and drug compliance will be summarized. Drug compliance categories of $\geq 105\%$, $>100\%$ to $<105\%$, $>90\%$ to $\leq 100\%$, $>80\%$ to $\leq 90\%$, $>70\%$ to $\leq 80\%$, and $\leq 70\%$ will also be presented.

A by-patient listing of exposure and compliance measures will be produced for SAF Analysis Set.

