6.5 Dose modification

Study treatment should be interrupted if the patient reports any treatment-related severe AE. Therapy should only be restarted after approval by the Medical Monitor.

If therapy is restarted, the same dose should be administered as that prior to occurrence of the AE. If the patient is still having tolerability issues and an AE reoccurs, the dose may be reduced from 2 tablets of study treatment bid to 1 tablet of study treatment bid, without breaking the study blind.

If another AE occurs after the study treatment dose reduction, study treatment will be permanently discontinued and the subject followed until the end of the study.

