6.3. Protocol Deviations

Protocol deviations will be recorded in the clinical trial management system.

Protocol deviations will be identified and classified as major protocol deviations prior to database lock and final unblinding. Major deviations are those deviations that significantly impact efficacy and result in the removal of patients from the PP Analysis Set. Major protocol deviations may include but are not limited to:

- Violation of Inclusion/Exclusion Criteria
- Study drug compliance $\leq 80\%$ or $\geq 105\%$
- Use of prohibited therapies
- Incorrect treatment

Major protocol deviations will be summarized by cohort and deviation category. Protocol deviations will be listed for the ITT Analysis Set by assigned treatment.

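### The SAP compliance formula flags patients who follow a permitted dose reduction or interruption and scores early stoppers at 100%, so it does not fit its use as a per-protocol criterion

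*SAP*

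**What the plan says.** SAP 6.8 builds compliance from three pieces.

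- **Duration.** "The duration of exposure to study drug is calculated as date of last dose of study drug taken" minus the date of first dose, plus 1.
- **Denominator.** "The planned total number of tablets during exposure is defined as duration of exposure x 4".
- **Numerator.** "The actual total number of tablets taken during exposure is calculated as the total number of tablets given" minus the number returned.

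Compliance is then "actual total number of tablets taken during exposure / planned total number of tablets taken during exposure x 100" percent. The same section gives the planned course: "Patients will be randomized to receive for a total of 4 weeks BOS-589" or placebo.

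SAP 6.3 lists compliance of 80% or less, or 105% or more, among the deviations that may be classed as major, and adds: "Major deviations are those deviations that significantly impact efficacy and result in the removal of patients from the PP Analysis Set". Under SAP 6.1 the PP set otherwise needs only one dose. The 6.3 list does not name early discontinuation.

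Protocol 6.5 directs interruption for a treatment-related severe adverse event. After restart and recurrence, "the dose may be reduced from 2 tablets of study treatment bid to 1 tablet of study treatment bid". Protocol 7.2 adds a further route to suspension and possible reduction. Protocol 7.1 keeps patients who stop drug in the study. SAP sections 6 and 7 run all efficacy analyses in both the ITT and PP sets.

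**The concern.** The denominator charges four tablets for every calendar day between first and last dose, whatever was prescribed on that day, and it ends at the last dose actually taken. This goes wrong in two opposite directions.

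A patient who does exactly what Protocol 6.5 asks can be recorded as non-compliant. Reductions and interruptions follow adverse events, so any resulting PP exclusions depend on tolerability and may differ by arm.

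A patient who stops permanently, having taken everything up to that point, is recorded as fully compliant. That patient can enter the PP analysis of a 4-week effect with much less than 4 weeks of treatment.

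The compliance table in SAP 6.8 is a result in its own right, so it would also misdescribe adherence.

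**Working it through.** The plan reports no compliance figure to reproduce, so the SAP formula is applied directly.

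**Inputs.** Planned course 28 days at 4 tablets per day = 112 tablets (SAP 6.8). Reduced dose 2 tablets per day and interruption 0 per day (Protocol 6.5). Flag at 80% or less, or 105% or more (SAP 6.3). Adherence to what was prescribed is taken as perfect, and the last dose falls on Day 28 unless the patient stops.

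**Formulas.**

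- Reduction from Day r to Day 28: [4(r − 1) + 2(29 − r)] / 112
- Interruption of g days, then restart at full dose: (28 − g) / 28
- Interruption of g days, then reduction from Day r: [4(r − 1 − g) + 2(29 − r)] / 112
- Permanent stop on Day d, all tablets taken: 4d / 4d

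| Scenario | Calculation | Score | Flagged |
|---|---|---|---|
| Reduced from Day 10 | 74/112 | 66.1% | yes |
| Reduced from Day 17 | 88/112 | 78.6% | yes |
| Reduced from Day 18 | 90/112 | 80.4% | no |
| Interrupted 5 days | 23/28 | 82.1% | no |
| Interrupted 6 days | 22/28 | 78.6% | yes |
| Interrupted 3 days, reduced from Day 23 | 88/112 | 78.6% | yes |
| Stopped Day 10 | 40/40 | 100% | no |
| Stopped Day 15 | 60/60 | 100% | no |

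The combined row matters because Protocol 6.5 places a reduction after an interruption and restart.

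There are exceptions among early stoppers. If only one dose is taken on the final day, a Day 1 stop scores 2/4 = 50% and a Day 2 stop 6/8 = 75%, both flagged. A Day 3 stop scores 10/12 = 83.3% and is kept. An early stopper who does not return tablets could also exceed 105%.

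**What an early stopper contributes at Day 29.** SAP 7 averages the 7 days before the Day 29 visit and accepts that visit within 14 days either side of calculated Day 29, that is, Days 15 to 43. Visit 7 in the Protocol schedule serves as Day 29, End of Treatment and Early Termination. Three cases follow.

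- **Prompt Visit 7 on or after Day 15.** The score is largely on drug, but after a shortened course. A Day 15 visit averages Days 8–14.
- **Prompt Visit 7 before Day 15.** The visit falls outside the window, so there is no Day 29 score, although the patient remains in the PP set.
- **Visit 7 on schedule after stopping.** A Day 10 stopper seen on Day 29 is averaged over Days 22–28, all off drug.

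**The case against.** Four points deserve weight.

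- **Exclusion is not automatic.** A reader might infer that the PP set will drop every patient who followed a permitted dose change. The documents do not say that. The SAP 6.3 list is permissive and open-ended, and SAP 6.1 has PP criteria finalized and documented before lock and unblinding. This stands. However, SAP version 1.2 contains neither an exemption nor an early-stop rule, so the written threshold is all there is to apply.
- **Early stoppers are not generally off drug in the assessment week.** A reader might infer that they are. Protocol 7.1 and the schedule footnote on early termination ask for Visit 7 procedures at or near discontinuation, and the 14-day window removes visits before Day 15. This stands for patients seen promptly. Protocol 7.1 also asks for remaining procedures to be completed, so an off-drug week is possible but not the rule. In both cases with a usable score, it follows less than 4 weeks of therapy.
- **Removing under-dosed patients may be intended.** A PP set can aim at the effect of the assigned dose, and a half-dosed patient did not receive it. That is a legitimate choice, but it is one about exposure and should be stated as such. It also sits badly with keeping a patient who stopped on Day 10.
- **Size is unknown.** The documents give no expected frequency of reductions, interruptions or stops. The only earlier human data reported, 14 days at up to 200 mg bid, describe the drug as generally well tolerated. ITT is untouched.

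**Conclusion.** The point holds as a defect in a stated formula. Under SAP 6.8, full adherence to a Protocol 6.5 reduction starting by Day 17, or to a directed interruption of six or more days with restart, gives 78.6% or less and meets the SAP 6.3 threshold. Shorter interruptions combined with later reductions can do the same. A permanent stop before Day 28 with all tablets taken gives 100%, and the patient stays in the PP set unless another deviation applies.

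The percentages assume a 28-day course, exact tablet return and perfect adherence to what was prescribed. The consequence for PP membership assumes that the listed threshold is applied as written. How many patients would be affected cannot be estimated from the documents. The reach is limited to the PP analyses and the compliance summary. That makes this a correction worth making before unblinding, not a threat to the primary ITT result.

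**What to change.** 1. **SAP 6.8.** Divide tablets taken by tablets prescribed on each day, using documented Protocol 6.5 reductions and protocol-directed interruptions, so that compliance measures adherence. A patient reduced from Day 10 then scores 74/74 = 100% instead of 66.1%.
2. **SAP 6.1 and 6.3.** Add a separate PP exposure criterion, fixed before unblinding, measured against the planned 28 days (112 tablets) and not truncated at the last dose. A new denominator cannot do both jobs. With interruption on Days 18–27 and restart on Day 28, adherence is 72/72 = 100% although the patient was off drug for most of the assessment week. Exposure is 72/112 = 64.3%.
3. **Cases the criterion must settle.** Stops on Days 23–27 pass an 80% limit on 112 tablets (Day 22: 88/112 = 78.6%; Day 23: 92/112 = 82.1%). The SAP should also say how it treats interruptions never restarted, interruptions covering the Day 29 assessment week, and patients on a permitted reduction.
4. **Reconcile** SAP 6.3 and 6.8 with Protocol 6.5 and 7.1. No dosing or stopping rule needs to change.

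The cost is SAP wording and some programming. Protocol 6.6 already requires deviations from the prescribed regimen to be recorded on the CRF. Some patients will move in or out of the PP set, which may become slightly smaller. An exposure rule can still remove a patient whose discontinuation the protocol required, but it would do so as a declared exposure limit and not as non-compliance.

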7. EFFICACY

Efficacy analyses will be conducted using the ITT and PP Analysis Sets.

All available efficacy data will be provided in by-patient data listings on all ITT patients.

The efficacy objectives of the study are to evaluate the effect of BOS-589, relative to Placebo after 4 weeks of therapy, on pain, defecation, and key IBS-D related signs and symptoms.

During the 4 weeks of the double-blind treatment phase, patients will be required to access their electronic diary every day, preferably at the same time each day, to record IBS-D symptom data and information related to their bowel function and rescue medication use.

For all efficacy endpoints, the Day 29 visit change from baseline is the main timepoint of interest. However, unless stated otherwise, data will be presented for each planned visit (Baseline/Day 1, Day 8, Day 15, Day 22, Day 29, and Day 43).

For efficacy endpoints collected daily, the baseline score will be the average of non-missing scores reported for the last 7 days prior to the date where eligibility and run-in criteria pertaining to IBS-D symptom and bowel function have been met. The Day 29 visit score will be the average of non-missing scores reported during the 7 days prior to the Day 29 visit. The Day 8 visit, Day 15 visit, Day 22 visit, and Day 43 visit scores are calculated in a similar manner. If there are missing daily scores on any day, the visit score will be averaged from all the non-missing values during the 7 days prior to the visit. No imputation of the missing values will be made. For the Day 29 calculation only, a window of ± 14 days relative to actual calculated day 29 from dosing will be applied such that any Day 29 visit occurring outside that window will be excluded.

Sponsor: Boston Pharmaceuticals, Inc.
Protocol Number: BOS-589-201
Version and Date: Version 1.2 12NOV2020

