1.3 Schedule of Activities

Table 1. Schedule of Activities

Procedures	Pre-treatment		Treatment					Follow-up	
	Screening Days -36 to -1, Study Visit 1	Run-in Period ^a Days -15 to -1, Study Visit 2	Baseline Day 1, Study Visit 3	Day 8 (± 1 day) Study Visit 4	Day 15 (± 1 day) Study Visit 5	Day 22 (± 1 day) Study Visit 6	Day 29 (± 1 day) End of Treatment ^b /Early Termination ^b Study Visit 7	Day 43 (± 3 days) End of Study Study Visit 8	
Informed consent	X								
Demographics	X								
Medical and surgical history	X								
Rome IV assessment	X								
Concomitant medication review	X	X	X	X	X	X	X	X	
Adverse event review and evaluation		X	----- continuous -----					X	
Physical examination ^c	X		X				X		
Height, weight, and body mass index	X ^d		X		X		X	X	
Vital signs	X		X	X	X	X	X	X	
12-lead electrocardiogram	X						X		
Clinical safety laboratory tests ^e	X		X		X		X	X	
HIV, HCV/HBV testing	X								
Urine pregnancy test	X		X				X	X	
C-reactive protein and erythrocyte sedimentation rate tests	X		X		X		X	X	
Biomarker sample collection			X		X		X	X	
Pharmacokinetic sample collection ^f			X	X	X	X			
Worst abdominal pain	X	X ^g	X	----- ^h -----					X ^h
Bristol Stool Form Scale	X	X ^g	X	----- ^h -----					X ^h

Procedures	Pre-treatment		Treatment					Follow-up
	Screening Days -36 to -1, Study Visit 1	Run-in Period ^a Days -15 to -1, Study Visit 2	Baseline Day 1, Study Visit 3	Day 8 (± 1 day) Study Visit 4	Day 15 (± 1 day) Study Visit 5	Day 22 (± 1 day) Study Visit 6	Day 29 (± 1 day) End of Treatment ^b /Early Termination ^b Study Visit 7	
Spontaneous bowel movements (total number of stools)		X ^g	X ^h	----- ^h	----- ^h	----- ^h	----- ^h	X ^h
IBS-GS		X ^g	X ^h	----- ^h	----- ^h	----- ^h	----- ^h	X ^h
Rescue medications		X ^g	X ^h	----- ^h	----- ^h	----- ^h	----- ^h	X ^h
IBS-SS			X				X	X
Eligibility review	X		X					
Randomization			X					
Administration of investigational product			Day 1	-----	-----	-----	-----	Day 28

HBV = hepatitis B virus; HCV = hepatitis C virus; HIV = human immunodeficiency virus; IBS-GS = Irritable Bowel Syndrome Global Scale;
 IBS-SS = Irritable Bowel Syndrome Severity Score.

^a Run-in may be extended by up to one week in accordance with the investigators judgement. The full 5 week (Days -36 to -1) may be used to randomize eligible patients. However, efforts should be made to randomize eligible patients within 1 to 3 days after completing run-in period.

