8.3.1 Worst Abdominal Pain

Throughout the 4 weeks of the double-blind treatment phase, patients will be asked to rate their WAP in the past 24 hours. The patient-reported WAP in the past 24 hours will be recorded on a 0 to 10 scale, where 0 corresponds to no pain and 10 corresponds to worst imaginable pain.

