5.2. Reference Dates

Reference dates are defined as follows:

- Screening date is defined as the electronic case report form (eCRF) provided visit date on which a patient was screened for trial entry.
- Informed consent date is defined as the eCRF provided date of informed consent from the informed consent page.
- Run-in period start date is defined as earliest date of eCRF provided visit date from the Run-in period page.
- Run-in period end date is defined as eCRF provided date of randomization -1 from the randomization page.
- Treatment start date is defined as the date of first dose of any study drug.
- Treatment end date is defined as the date of last dose of any study drug.
- Age will come directly from the eCRF which is integrated from IWRS based on the informed consent date.

Sponsor: Boston Pharmaceuticals, Inc.
Protocol Number: BOS-589-201
Version and Date: Version 1.2 12NOV2020

- Safety data, such as AEs and laboratory assessments, will use the treatment start date as a reference date.
- Efficacy data will use the treatment start date as a reference date.
- Study day will be based on treatment start date as a reference date. Study Day 1 will be the day patients start the first dose of study drug.

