5.3. Study Day and Duration Variables

Reference date calculations will generally be defined as the following, assuming non-missing dates:

- date of interest – reference date + 1 when the date of interest \geq reference date;
- otherwise, date of interest – reference date.

If either date is missing, reference date calculations will not be performed. Date imputation will be performed as identified in Section 5.6.

Study day will either have a negative value if collected before dosing or a positive value if collected on or after the day of drug dosing; there will be no study day zero.

Duration of time is dependent on reference dates and will be calculated in a manner similar to that of the reference date calculation. Duration on study is defined as the end of study date – informed consent date + 1. Duration of treatment is defined as treatment end date – treatment start date + 1, where treatment end date is the date of last dose of study drug. Patients still receiving ongoing treatment or participating in study follow up at the time of analysis will use imputed treatment end and end of study dates as described in Section 5.7.

Durations reported in days will be calculated as measure date – reference date + 1. When reporting in months the result will be divided by 30.4375; for reporting in weeks it will be divided by 7; and for reporting in years it will be divided by 365.25.

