5.5. Baseline and Post-Baseline Changes

Unless stated otherwise, baseline and post-baseline change values will be based on the following:

Sponsor: Boston Pharmaceuticals, Inc.
Protocol Number: BOS-589-201
Version and Date: Version 1.2 12NOV2020

- Baseline will be based on the last non-missing value (including unscheduled assessments) collected prior to or on the treatment start date/time for measures collected prior to the treatment.
- Post-baseline values will be those collected after the date/time of first dose of study drug.
- Change from baseline is defined as: value – baseline value.
- Percentage change from baseline is defined as: $(\text{value} - \text{baseline value}) / \text{baseline value} \times 100\%$.
- Maximum change will be based on the change from baseline value to the maximum value for all post-baseline assessments collected during the on-treatment period, scheduled or unscheduled, using the formulas above.
- Minimum change will be based on the change from baseline value to the minimum value for all post-baseline assessments collected during the on-treatment period, scheduled or unscheduled, using the formulas above.

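### Read literally, the SAP's Day 8 diary score can count reports collected before the first dose, and SAP 7 is not reconciled with SAP 5.5; Day 29 is unaffected

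*SAP*

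**What the plan says.** The current SAP (version 1.2), Section 7, defines the visit score for daily diary items through Day 29: "The Day 29 visit score will be the average of non-missing scores reported during the 7 days prior to the Day 29 visit". It then extends the rule: "The Day 8 visit, Day 15 visit, Day 22 visit, and Day 43 visit scores are calculated in a similar manner". Gaps are not imputed; "the visit score will be averaged from all the non-missing values during the 7 days prior to the visit".

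The day numbering comes from SAP 5.2, "Study Day 1 will be the day patients start the first dose of study drug", and SAP 5.3, "there will be no study day zero". The Protocol's Schedule of Activities (1.3) lists "Day 8 (± 1 day) Study Visit 4", so attendance on Day 7, 8 or 9 is in window. SAP 7 sets an analysis window of its own for Day 29 only.

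Each report looks back one day: in Protocol 8.3.1, "patients will be asked to rate their WAP in the past 24 hours". The diary is completed daily from run-in onward at no fixed clock time, and the first dose is given at the clinic on Day 1 (Protocol 6.6).

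SAP 5.5, which applies unless something else is stated, says: "Post-baseline values will be those collected after the date/time of first dose of study drug".

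**The concern.** Seven days before a Day 8 visit reaches back to Day 1. Seven days before a Day 7 visit reaches back to Day -1, which is run-in. A programmer following SAP 7 alone would average those reports into a score labelled post-baseline; a programmer who also applied SAP 5.5 would drop those collected before dosing. Both could claim to have followed the plan, and their Day 8 tables would differ.

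Under the literal reading the first-week effect is pulled toward zero, by an amount that depends on which permitted day the patient attended. Two patients with the same response could be classed differently as weekly responders. If the run-in criteria are met on Day 1 itself, the Day -1 report also lies in the baseline week, so one report sits on both sides of the change score. The rule applies to worst abdominal pain (WAP), both stool-form items, stool frequency, the global symptom score and the weekly responder.

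**Working it through.** **The plan's own figures.** The documents give no figure for Day 8. The one relevant calculation is the power for the first hypothesis at Day 29 (SAP 3.4: difference 1.6, SD 3, two-sided 0.05, N = 120, so 40 placebo and 80 pooled active). The standard error is 3 × √(1/40 + 1/80) = 0.581, and 1.6/0.581 = 2.754. Power is Φ(2.754 − 1.960) = 78.6%, consistent with the stated approximate 80%. This point does not disturb that figure: a visit on Day 29 uses Days 22–28, and the earliest visit that SAP 7 accepts (29 − 14 = Day 15) uses Days 8–14.

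**Step 1: days entering the Day 8 score.** List the seven study days before the visit, with Day -1 followed directly by Day 1.

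| Visit on | Days averaged | Reports dated Day 1 or earlier |
|---|---|---|
| Day 7 | -1, 1–6 | 2 |
| Day 8 | 1–7 | 1 |
| Day 9 | 2–8 | 0 |

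**Step 2: dilution.** Let s be the pre-dose share of the seven reports. Assume pre-dose reports sit at the baseline level and the effect is constant from the first dose; the documents state neither. The observed change is then (1 − s) times the true on-drug change. How far the Day 1 report is pre-dose depends on when it was entered, so a range is shown.

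| Visit on | Day 1 report wholly pre-dose | Half pre-dose | Counted as post-dose |
|---|---|---|---|
| Day 7 | 2/7 = 28.6% | 1.5/7 = 21.4% | 1/7 = 14.3% |
| Day 8 | 1/7 = 14.3% | 0.5/7 = 7.1% | 0% |
| Day 9 | 0% | 0% | 0% |

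For scale, a true 1.6-point difference would appear as 1.6 × 6/7 = 1.37 if all visits fell on Day 8, or 1.6 × 5/7 = 1.14 if all fell on Day 7, with the Day 1 report wholly pre-dose.

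**Step 3: responder criteria (SAP 7.3.1).** The fall needed on treated days is the threshold divided by (1 − s).

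- Pain, 30%: 0.30 × 7/6 = 35% (s = 1/7); 0.30 × 7/5 = 42% (s = 2/7).
- Stool, 50%: 0.50 × 7/6 = 58.3%; 0.50 × 7/5 = 70%.

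Example: baseline 5.0 and on-drug WAP 3.4 is a true fall of 1.6/5.0 = 32%. With one report at 5.0 and six at 3.4, the score is (5.0 + 6 × 3.4)/7 = 3.63, a fall of 27.4%. The patient is counted as a non-responder.

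**Step 4: missing entries.** The denominator shrinks when diary days are missing. With two post-dose days missing, the share becomes 1/5 = 20% (Day 8 visit) or 2/5 = 40% (Day 7 visit), so 29% is a ceiling only for complete diaries and in-window visits.

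**The case against.** The strongest reply is that SAP 5.5 already answers the point. SAP 7 sets a look-back and never says that pre-dose reports count as post-baseline, so the two can be read together: look back seven days and keep what was collected after dosing. On that reading the Day -1 report and a Day 1 report entered before dosing both drop out. This is a fair reading, but not the only one. SAP 5.5 gives way where something else is stated, and SAP 7 states a specific rule without an exclusion.

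Second, the SAP generally treats Day 1 as on-treatment: the on-treatment period starts on the treatment start date (5.4), the rescue-medication treatment period begins on Day 1 (6.7), and Day 1 adverse events without an onset time are treatment-emergent (9.1). With visits on their nominal days, the windows cover Days 1–7, 8–14, 15–21 and 22–28 exactly. This stands, and it argues against discarding every Day 1 entry. It does not justify using an entry made before the first dose.

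Third, little depends on Day 8. Day 29 is the main timepoint, Day 8 WAP is summarized descriptively, secondary p-values are descriptive, and the responder test is exploratory and for reference. The rule is the same in all blinded arms, so under the stated assumptions the dilution runs toward no effect. All of this stands and sets the severity.

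A reader might infer that every first-week effect is diluted by 14–29%. The documents do not support that: a Day 9 visit is in window and gives 0%, and a Day 1 report made after dosing is at most partly pre-dose. A reader might also take Day 8 as the only view of onset. Protocol 9.4.1.2 tabulates stool form and stool frequency by study day, and SAP 7 lists all efficacy data by patient.

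**Conclusion.** The point holds as an unreconciled conflict between SAP 7 and SAP 5.5, confined to Day 8. Under the literal rule, and with complete diaries, the dilution of the first-week change is 0% for a Day 9 visit, up to 14% for a Day 8 visit and up to 29% for a Day 7 visit. The effective pain-responder criterion is up to 35% or 42% in the last two cases. These sizes rest on pre-dose reports being at the baseline level and a constant effect from the first dose. They also classify reports by when they were collected: a Day 2 entry made earlier in the day than the Day 1 dose would still recall some pre-dose hours.

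The affected outputs are the Day 8 summaries, plots, reference tests and exploratory responder tests. It would be wrong to infer any effect on the primary analysis; the Day 29 endpoint and the four hierarchical hypotheses are untouched. Severity: minor.

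**What to change.** Add to SAP 7: *Diary entries collected before the date/time of first dose are not used in any post-baseline visit score (SAP 5.5); the 7-day look-back otherwise applies.*

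A Day 1 entry made after dosing may stay in, which agrees with SAP 5.5; note that its 24-hour recall is partly pre-dose. The documents do not say whether the diary stores an entry time, so the SAP should also state how a Day 1 entry without a time is classed.

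For the Day 8 stool responder, compare the proportion of reported days with a Type 6 or 7 stool instead of a raw count. Otherwise the shorter window would favor response. For example, 7 of 7 such days at baseline against 3 of 5 at Day 8 is a 57% fall in count (4/7) but only a 40% fall in proportion (1 − 0.6).

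The cost is one sentence for the score and one for the responder. The Day 8 score would rest on five or six diary days for some patients: five for a Day 7 visit with a pre-dose Day 1 entry, and six for a Day 7 visit with a post-dose Day 1 entry or a Day 8 visit with a pre-dose one. That is a small loss of precision at a visit that is not the main timepoint.
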